#### ***Criterion for success of each intervention in each period.***

0-24 hours: for each of bupivacaine and exparel, success will be concluded if found to be superior over placebo (i.e., less opioid consumption). As well, exparel or bupivacaine will be concluded better than the other if found superior on opioid consumption.

24-48 hours: exparel will be concluded successful if found better than both placebo and bupivacaine in the 24-48 hours opioid consumption.

## **Secondary Aims**

### **Secondary Aim 1:**

To assess the duration of the local analgesia (determined by pinprick and cold) in all four quadrants with liposomal bupivacaine, plain bupivacaine, and placebo after major abdominal surgery.

Hypothesis. Abdominal wall analgesia from four-quadrant TAP blocks with single-shot liposomal bupivacaine lasts longer after major abdominal surgery than the same blocks with plain bupivacaine or placebo. Our major outcome will be time from end of the block until abdominal wall sensation with both ice and pinprick recovers in at least six of eight designated locations. Two sequential evaluations will be needed to be negative and first negative time point will be accepted as the return of sensation.

### **Secondary Aim 2:**

To compare the effect of liposomal bupivacaine, plain bupivacaine, and placebo on pain after surgery in first 72 hours or the duration of hospitalization if shorter.

Hypothesis. Pain scores over the initial 72 hours or duration of hospitalization after major abdominal surgery are lower when four-quadrant TAP blocks are performed with liposomal bupivacaine than with plain bupivacaine or placebo. Pain will be assessed on a 0-10-point scale (10 points being worst) at 4-hour intervals while patients are awake. A difference of at least 1.2 points will be considered clinically meaningful.

### **Secondary Aim 3:**

To evaluate TAP blocks with liposomal bupivacaine, plain bupivacaine, and placebo on opioid consumption in 24 to 48 hours.

Hypothesis. Opioid consumption from the 48 to 72 hours or duration of hospitalization after major abdominal surgery is less when four-quadrant TAP blocks are performed with liposomal bupivacaine than with plain bupivacaine or placebo. Opioid consumption will be evaluated as morphine sulfate equivalents; a difference of at least 10 mg will be considered to be a clinically meaningful difference.

## **Tertiary**

**Tertiary Aim 1.** To compare the effect of liposomal bupivacaine, conventional bupivacaine, and placebo on a composite of opioid-related postoperative side effects.

**Hypothesis.** Opioid-related side effects over the initial 72 hours or duration of hospitalization after major abdominal surgery are less common when four-quadrant TAP blocks are performed with liposomal bupivacaine than with plain bupivacaine or placebo. Opioid-related side effects will be evaluated as composite of events, and a difference of 20% in incidence will be accepted as clinically important difference.

**Tertiary Aim 2.** To compare the effect of liposomal bupivacaine, conventional bupivacaine, and placebo on satisfaction with their pain treatment after first 72 hours or the duration of hospitalization if shorter.

**Hypothesis.** Patients are more satisfied with pain management over the initial 72 hours or duration of hospitalization after major abdominal surgery when four-quadrant TAP blocks are performed with liposomal bupivacaine than with plain bupivacaine or placebo.

**Tertiary Aim 3.** To assess total and specific costs of hospital care in patients receiving TAP with liposomal bupivacaine vs. those with plain bupivacaine following abdominal surgery.

**Tertiary Aim 4.** To compare the effects of TAP blocks with liposomal bupivacaine, plain bupivacaine and placebo on patients' pain with movement for 72 hours/discharge surgery.

**Hypothesis.** Pain scores with movement over the initial 72 hours or duration of hospitalization after major abdominal surgery are lower when four-quadrant TAP blocks are performed with liposomal bupivacaine than with plain bupivacaine or placebo. Pain will be assessed on a 0-10-point scale (10 points being worst) at 12-hour intervals while patients are elevating their leg. A difference of at least 1.2 points will be considered clinically meaningful.

**Tertiary Aim 5.** To compare the effects of TAP blocks with liposomal bupivacaine, plain bupivacaine and placebo on patients' mobility for 72 hours/discharge surgery.

**Hypothesis.** Total amount of mobilization over the initial 72 hours or duration of hospitalization after major abdominal surgery are higher when four-quadrant TAP blocks are performed with liposomal bupivacaine than with plain bupivacaine or placebo.

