## Specific Aims

Pain management after major abdominal surgery remains challenging. The best-accepted traditional analgesic approach is continuous epidural analgesia. However, epidural analgesia is rapidly being replaced by transversus abdominis plane (TAP) blocks. TAP infiltration is an alternative to epidural blocks for providing postoperative analgesia to the anterior abdominal wall. TAP infiltrations are relatively easy to perform, generally safe, and can be performed in patients who are anti-coagulated. TAP infiltration can be performed as a single injection, or a catheter can be inserted for continuous local anesthetic infusion.

Single shot plain bupivacaine is often used for TAP blocks, but plain bupivacaine provides <24 hours of analgesia. Catheters provide analgesia for longer, but they are difficult to position properly and difficult to maintain in the proper anatomical location. An alternative to TAP catheters is infiltration of liposomal bupivacaine which, in other sites, lasts up to three days. But whether liposomal bupivacaine is preferable to plain bupivacaine for TAP blocks remains controversial, with available studies being sparse and inconclusive.

We therefore proposed to compare single-shot TAP infiltration with liposomal bupivacaine, plain bupivacaine, and placebo on length of anesthetic effect determined by the opioid consumption. We will evaluate the following specific aims, all of which will be assessed over 72 hours, or the duration of hospitalization if shorter:

**Primary Aim 1:** To assess the relative effects of TAP blocks with liposomal bupivacaine, plain bupivacaine and placebo on cumulative opioid consumption in first 24 hours with TAP blocks.

**Primary Aim 2:** To assess the relative effects of TAP blocks with liposomal bupivacaine, plain bupivacaine and placebo on cumulative opioid consumption in 24 to 48 hours with TAP blocks.

**Secondary Aim 1:** To assess the relative effects of TAP blocks with liposomal bupivacaine, plain bupivacaine and placebo on the duration of abdominal wall analgesia (determined by pinprick and cold).

**Secondary Aim 2:** To assess the relative effects of TAP blocks with liposomal bupivacaine, plain bupivacaine and placebo on pain after surgery in first 72 hours.

**Secondary Aim 3:** To assess the relative effects of TAP blocks with liposomal bupivacaine, plain bupivacaine and placebo on cumulative opioid consumption 48 to 72 hours.

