b. Nerve block and liposomal bupivacaine

Single-shot peripheral nerve blocks with liposomal bupivacaine have distinct advantages compared to a continuous catheter. Specifically, patients given liposomal bupivacaine will not require infusion pumps and cannot develop catheter-related infection, hematoma, or dislodgement. Because liposomal bupivacaine was only recently approved for peripheral nerve blocks, and only at one site, there is currently little information about the approach. However, Hadzic et al. compared liposomal bupivacaine to placebo for femoral nerve blocks and found lower pain score and decreased opioid consumption were reduced. A retrospective analysis of peripheral nerve blocks with liposomal bupivacaine suggests that safety and the side effect profile are similar with bupivacaine and placebo.

Intercostal nerve blocks with liposomal bupivacaine were evaluated after thoracic surgeries and compared with plain bupivacaine. Liposomal bupivacaine reduced hospital duration — but curiously without a reduction in postoperative pain score or opioid use. Further studies are clearly needed to evaluate the efficacy of liposomal bupivacaine in nerve blocks.

c. TAP block and liposomal bupivacaine

So far only a few trials directly compare liposomal and plain bupivacaine for TAP blocks, and there is no consensus among them. According to a Cochrane systemic review, evidence is lacking for the efficacy of liposomal bupivacaine in TAP blocks, and concludes that there is no advantage to use of liposomal bupivacaine for this indication. It is important to recognize, though, that this conclusion is based on lack of evidence for benefit rather than robust evidence against. In another study, Guarre et al. compared

plain and liposomal bupivacaine in TAP blocks for laparoscopic colorectal surgery. Patients treated with liposomal bupivacaine required less opioid, had earlier return of bowel function, and left the hospital sooner. Hutchins et al. showed that TAP blocks with liposomal bupivacaine provided long-lasting analgesia compared to plain bupivacaine for laparoscopic-assisted donor nephrectomy, and reduced nausea and vomiting and the duration of hospitalization. In contrast, Ha et al. compared liposomal bupivacaine and plain bupivacaine in TAP blocks for breast reconstruction and reported no benefit.

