#### **B. Setting and Population**

##### **Inclusion criteria:**

- (1) Written informed consent;
- (2) 18-85 years old;
- (3) ASA Physical Status 1-3;
- (4) Scheduled for elective open or laparoscopic-assisted abdominal surgery;
- (5) Anticipated hospitalization of at least three nights;
- (6) Expected requirement for parenteral opioids for at least 72 hours for postoperative pain;
- (7) Able to use IV PCA systems.

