**Placebo group;** patients will receive total of 80 ml of normal saline, injected 20 ml in each of the four-quadrant sites.

General anesthesia will be induced using propofol or etomidate, fentanyl, and rocuronium to facilitate intubation. Anesthesia will be maintained with sevoflurane or isoflurane, along with opioids and muscle relaxants as clinically indicated. However, intraoperative analgesic use will be limited to fentanyl, a short-acting opioid.

Postoperatively, patients will be given intravenous patient-controlled analgesia and nurses will be free to give additional opioid as clinically indicated. Hydromorphone will be the default drug, but fentanyl will be substituted if necessary. Clinicians blinded to trial drug will adjust analgesic management as necessary in an effort to keep verbal response pain scores (details below) <4 points on a 0-10 scale, with 10 being worst pain. When patients no longer need PCA, they will be switched to as-needed hydromorphone or fentanyl.

A single dose of dexamethasone (4-8 mg) will be given to all patients for PONV prophylaxis, and inhaled steroids will be permitted as necessary to treat reactive airway disease. The use of non-steroidal anti-inflammatory drugs and gabapentinoids will be allowed as part of the ERAS approach (enhanced recovery after surgery) according to hospital's clinical practice. Other opioid-sparing medications such as ketamine and lidocaine patches will not be permitted through the initial 72 postoperative hours. Vital

signs and patient activity will be continuously monitored and recorded with a wireless monitor (ViSi mobile, Sotera Wireless, San Diego, CA). Monitoring will be started about 30 minutes after arrival in the postanesthesia care unit and continued for 72 hours while patients remained hospitalized. Clinicians will be blinded to continuous monitoring data; clinical decisions therefore will be guided by routine intermittent vital signs which were typically obtained at 4-hour intervals.

Patients will be allowed to receive prophylactic anti-emetic (first choice ondansetron) intraoperatively based on the risk assessment for nausea and vomiting. Postoperative anti-emetics for symptomatic treatment will also be allowed; again ondansetron will be the first choice.

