### ***Tertiary Outcome 5.***

Patient's mobility will be obtained from VISI monitoring device for 72 hours/discharge surgery

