### **Tertiary Outcomes.**

Groups will be compared on the collapsed composite of opioid-related side effects in the first 72 hours after surgery using chi-square tests. Groups will be compared on satisfaction with pain management at using a 0-10 point scale at 72 hours, or upon discharge if earlier, using the Kruskal-Wallis test overall and Wilcoxon rank sum test between interventions.

**Economic Analysis.** Finally, if a treatment effect between the 2 local anesthetic TAP blocks is detected, we will conduct a cost-effectiveness analysis estimating the incremental cost-effectiveness ratio (ICER) as the mean difference in costs divided by the mean difference in the primary outcome of time to return of sensation [or an analogous ratio using summaries which best fit the distribution of the data]. Total cost of hospital care and specific care costs will be estimated from data in the electronic medical records database. Data obtained from electronic medical records will include: operation time, surgery type, intraoperative opioid consumption, postoperative opioid consumption in PACU and in ward, breakthrough pain medication requirements, pain scores in PACU and ward, requirement of oxygen in PACU and ward, pruritus, requirement of antihistaminic medications, requirement of naloxone, itching, ambulation time, flatus, ileus, bowel movements (first time documented), constipation, length of stay and any side effects or complications.

**Interim Analyses.** We will use a group sequential design to conduct interim analyses at each 25% of the planned enrollment to assess efficacy and futility of the intervention using a gamma spending function. Specifically, we will maintain the overall alpha level (monitoring efficacy) at 0.05 using gamma parameter of -4 [similar to O'Brien Fleming], and power at 90% (monitoring beta, type II error) using gamma parameter of 0 [more aggressive, similar to Pocock]. Under the alternative hypothesis (assuming a true 50% relative reduction in the primary outcome) the cumulative probability of crossing an efficacy (and futility in parentheses) boundary at the 1st through 4th analyses will be 0.09 (0.025), 0.39 (0.05), 0.75 (0.075) and 0.90 (0.10) as shown in **Figure 1**.

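### Mobility (Tertiary Aim 5) is framed as a total over a window that closes at discharge, so at equal hourly mobility the arm discharged earlier scores lower

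*Combined protocol and SAP*

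**What the plan says.** In section 2 (Study Objectives), the hypothesis for Tertiary Aim 5 is "Total amount of mobilization over the initial 72 hours or duration of hospitalization after major abdominal surgery are higher" with liposomal bupivacaine than with either comparator. The measure is therefore cumulative, and more counts as better.

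Section 3.E, Tertiary Outcome 5, gives the only source of data: "Patient's mobility will be obtained from VISI monitoring device for 72 hours/discharge surgery". It states no unit, no scaling and no rule for incomplete recording. Section 3.D says that monitoring starts about 30 minutes after arrival in the postanesthesia care unit and is "continued for 72 hours while patients remained hospitalized".

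Discharge before 72 h is foreseen. The Specific Aims introduce all aims as "all of which will be assessed over 72 hours, or the duration of hospitalization if shorter". The inclusion criteria (section 3.B) make it less likely, through "Anticipated hospitalization of at least three nights" and an expected need for parenteral opioids over the same 72 h.

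Section 3.F, Tertiary Outcomes, covers the side-effect composite ("Groups will be compared on the collapsed composite of opioid-related side effects in the first 72 hours after surgery using chi-square tests"), satisfaction and costs. It does not mention mobility.

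**The concern.** A sum collected only in hospital mixes two things: how active the patient is per hour, and how many hours were recorded. Nothing is added after discharge. If one arm goes home sooner, its totals shrink even when its patients are just as active hour for hour. Time with the monitor off acts in the same way.

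The protocol gives a reason to think that stay could differ by arm. Section 1.D cites a study of TAP blocks in laparoscopic colorectal surgery in which patients given liposomal bupivacaine "had earlier return of bowel function, and left the hospital sooner", and a donor-nephrectomy study that also reported shorter hospitalization. If that recurred, the bias would run against the arm that the hypothesis favours.

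Resting pain is treated differently. Section 3.F analyses it as a mean in a mixed model, and a mean does not fall merely because observation stops.

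**Working it through.** The documents state no effect size, SD, unit or discharge rate for mobility, so there is no figure of the plan to reproduce. The check is arithmetic on a cumulative total, under stated assumptions.

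**1. Break-even for one patient.** Assume a constant hourly rate, so total = rate × hours observed. A patient discharged at hour T ties a patient observed for 72 h only if the ratio of hourly rates is 72/T:

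- T = 48: 72/48 = 1.50
- T = 60: 72/60 = 1.20
- T = 66: 72/66 = 1.09

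A patient who is 20% more mobile per hour and leaves at 48 h scores 1.20 × 48/72 = 0.80 of the stayer's total. Leaving at 66 h, the same patient scores 1.20 × 66/72 = 1.10.

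**2. Share of the 72 h total captured.** Assume that leaving after two nights gives 45 h of data and after three nights 69 h. Hourly mobility is either flat or rises 1:2:3 over days 1 to 3.

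- 45 h: flat 45/72 = 0.625; rising (1 + 2 × 21/24)/6 = 2.75/6 = 0.458
- 69 h: flat 69/72 = 0.958; rising (1 + 2 + 3 × 21/24)/6 = 5.625/6 = 0.938

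**3. Ratio of arm means with no true difference.** If a share p leaves at 45 h and the rest at 69 h, the arm mean is p × share(45) + (1 − p) × share(69). For 25% versus 5%:

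- Flat: (0.25 × 0.625 + 0.75 × 0.9583)/(0.05 × 0.625 + 0.95 × 0.9583) = 0.8750/0.9417 = 0.929
- Rising: (0.25 × 0.4583 + 0.75 × 0.9375)/(0.05 × 0.4583 + 0.95 × 0.9375) = 0.8177/0.9135 = 0.895

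| Leaving at 45 h (assumed) | Flat | Rising | Artefact |
|---|---|---|---|
| 10% v 5% | 0.982 | 0.974 | 2-3% |
| 20% v 10% | 0.964 | 0.946 | 4-5% |
| 25% v 5% | 0.929 | 0.895 | 7-10% |

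**4. What happens to a real benefit.** Suppose the true hourly rate is 10% higher in the arm that leaves earlier.

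- 25% v 5% at 45 h: 1.10 × 0.929 = 1.02 (flat) or 1.10 × 0.895 = 0.98 (rising).
- Flat rate, early leavers at 48 h and others at 72 h, 10% leaving early in the comparator: with 30% leaving early, 1.10 × (0.7 × 72 + 0.3 × 48)/(0.9 × 72 + 0.1 × 48) = 1.10 × 64.8/69.6 = 1.02; with 40%, 1.10 × 62.4/69.6 = 0.99.
- The same with early discharge at 60 h: still 1.03 at 50% v 10% (1.10 × 66/70.8).

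**5. Would one whole-stay rate cure it?** Only if mobility is flat. With rising mobility, the average rate per day of observation is 2.75/(45/24) = 1.467 for the 45 h leaver and 5.625/(69/24) = 1.957 for the 69 h patient. At 25% v 5% the ratio of mean rates is (0.25 × 1.467 + 0.75 × 1.957)/(0.05 × 1.467 + 0.95 × 1.957) = 1.834/1.932 = 0.949. About 5% of artefact remains because early leavers contribute no late hours. The rate has to be taken within day.

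**The case against.** The best defence is that the plan contains no mobility analysis to criticise. The cumulative wording occurs once, in a hypothesis sentence; the aim itself and the measurement section say only mobility. No text tells the analyst to enter zero for hours after discharge. That is fair, and the missing metric and analysis are part of the point. But the hypothesis is the only place where the quantity is described, nothing else corrects it, and a sum over recorded hours has the same effect as entering zero.

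The second defence is eligibility. Patients are chosen for an anticipated three nights and an expected 72 h of parenteral opioid, so few should leave after two nights. This also stands. The criteria are expectations and not guarantees, but the larger splits above have no support in the documents and are illustrations only.

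A reader might infer more: that patients who recover and leave early necessarily score as less mobile, or that a true benefit would be reversed. The documents do not support either. At a given stay the total rises with mobility, and an early leaver whose hourly rate exceeds 72/T times a stayer's still scores higher. Nor is earlier discharge with liposomal bupivacaine established: section 1.D also cites a TAP trial in breast reconstruction that reported no benefit.

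**Conclusion.** The concern holds in limited form. Followed as written, the mobility measure depends on hours observed, and at equal hourly mobility it is biased against the arm with more discharges before 72 h. The direction is clear; the size cannot be computed from the documents. Under the assumed discharge times and splits the artefact runs from 2-3% to 7-10%. That is enough to attenuate a modest benefit. Turning a 10% benefit negative takes a large imbalance, such as 40% versus 10% leaving at 48 h with flat mobility, or 25% versus 5% leaving at 45 h with steeply rising mobility. This is the last of five tertiary aims, so the primary conclusions and the sample size are not touched. The change is worth making but not essential.

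**What to change.** - **Tertiary Aim 5 and Tertiary Outcome 5:** replace the cumulative total with activity per monitored hour, calculated within each postoperative day (0-24, 24-48 and 48-72 h).
- **Section 3.F, Tertiary Outcomes:** add a repeated-measures model with treatment and day. Take the contrast over 0-48 h, when nearly all patients should still be observed, as the main result. Avoid a single whole-stay rate, or an offset for monitored time without day in the model, because both leave the residual bias shown in step 5.
- **Reporting:** give monitored hours and the number discharged before 72 h by arm.

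The cost is a sentence in each of the two definitions and a short analysis paragraph, settled before unblinding, with no new study procedures. There are two limits. The 48-72 h estimate describes only patients still in hospital, who may be the slower to recover, and should be labelled so. Monitored hours must also be derivable from the monitor record; the protocol says that activity is recorded continuously but does not say that usable recording time is logged, so this needs confirming.

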### **3. Method and Study Design**

#### **A. Study Overview**

We propose a randomized double-blind trial comparing TAP blocks with liposomal bupivacaine, plain bupivacaine, and placebo in patients having elective abdominal surgery. The study will be performed at various Cleveland Clinic hospitals with IRB approval and written consent from patients. Study will be registered at ClinicalTrials.gov website before the first patient is enrolled.

#### **B. Setting and Population**

##### **Inclusion criteria:**

- (1) Written informed consent;
- (2) 18-85 years old;
- (3) ASA Physical Status 1-3;
- (4) Scheduled for elective open or laparoscopic-assisted abdominal surgery;
- (5) Anticipated hospitalization of at least three nights;
- (6) Expected requirement for parenteral opioids for at least 72 hours for postoperative pain;
- (7) Able to use IV PCA systems.

